The Fitbit activity tracker was chosen for this feasibility study due to its versatility and effectiveness within younger populations of children. The FitBit's ease of use, comfort, design and feedback features were important factors for all age groups (children and AYA). Researchers in some studies utilized the Fitbit activity tracker to assess adherence to home-based activity programs⁷⁵.

I. PROCEDURES

[figure not shown]
I.1 Overview

For this feasibility study, 40 pediatric patients with a diagnosis of ALL or LL who have a TNS of ≥ 3 at the end of four weeks of vincristine treatment will be enrolled from Riley Hospital for Children, Indiana University Health North Hospital, . Children and AYA will be recruited during their first four weeks after diagnosis and if they have a TNS ≥ 3 at the time of baseline (week 4-6 T1) they will be enrolled into the study. During T1 patients will complete all questionnaires, neuropathy exams, and provide blood samples and then again at week 14 (T2). Neuropathy exam may be performed during weeks 4 through 6 to accommodate regimented clinical visits. Exercise assessments will be performed on week 7. Subjects will check-in with the exercise therapist during weeks 9, 11, and 13 at a minimum, or once a week during the study if they choose (weeks 7-15). These in-

person sessions will take approximately 15 minutes, and the therapist will provide education, evaluate the subject's exercise plan, review exercises, set goals, and make plans to optimize adherence to the exercise program.

All study visits will take place before or after routine clinic visits so that patients and their families do not have to make additional trips to the four hospital sites. EX sessions will be completed by patients at home using instructional videos that will be given to participants during their study orientation.

I.2 Intervention timeline

I.3 Exercise (EX) Intervention

The EX intervention will include both an in-person exercise schedule and at-home video EX sessions (See Appendix I and II). The EX intervention will be designed and led by an AFAA (Athletics and Fitness Association of America) certified physical fitness trainer with fifteen years' experience and a professional with a PhD in an Exercise Science related field.

In-Person Exercise Sessions:

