The first session will be completed at one of the four hospital sites with the EX intervention specialist during the baseline visit. Patients will check-in with their intervention specialist during routine visits to one of the sites or phone on weeks 8, 10, and 12 at a minimum throughout consolidation treatment, or once per week if they choose (weeks 7-15). In-person sessions will last approximately 15 minutes each during which time the therapist will provide *education* on the importance of exercise for VIPN, review the exercises, reassess difficulty level, *set exercise goals* for the following week, and *plan* to reach these goals. Reviewing exercises will demonstrate that the patient has learned exercises through *observational learning* from the therapist and peer models on the exercise videos. In-person sessions will also allow the therapist to provide *reinforcement* for the patient's progress.

If the patient or the study team are unable to meet in person the intervention specialist will contact the patient via their prefer contact method (phone call, email, Skype). These sessions will follow the format of the in-person sessions. Education, assessment of difficulty level, set exercise goals and plan will all be discussed during the remote check-in.

Home Exercise Sessions:

At baseline, participants will have access to the exercise videos via the study website or they will be downloaded to the study tablet, with 3 chapters of EX sessions to be completed at home with video instruction. Patients will be asked to complete home EX sessions 6 times per week for 8 weeks (week 6 through week 13) during the consolidation phase of treatment. A Daily Exercise Log is available to record exercise chapters, fatigue level and time of day exercised (See Appendix III). Patients may choose their rest day each week. Each EX session will last approximately 15 minutes. The at-home videos will have the therapist and three children and AYA who are of similar age to the patients demonstrate the exercises. This design is critical for supporting the *observational learning* component of the intervention. Two videos will be available for the study: one for ages 5 – 10; one for ages 11 – 25.

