Six Minute Walk Test: The Six- minute walk test (6MWT) is used to assess subjects’ functional exercise capacity. This assessment will be conducted by an exercise professional during week 7 (T1) and week 15 (T2) physiological assessments. The 6MWT will be conducted following the American Thoracic Society Guidelines⁸⁸ and our standard operating procedures. Subjects will be asked to walk as far as possible for 6 minutes. They will be assessed on how far of a distance is walked over the course of these six minutes. Subjects will be allowed to slow down, stop and rest as needed. They will be asked to resume walking with they are able. This assessment will be performed at all sites.

Romberg Balance Test: The Romberg Balance is an assessment of the subjects balance and proprioception⁸⁹. The patient will be asked to remove their shoes, stand with their feet together, arms held to their side or crossed in front of their chest. They will be asked to stand quietly with their eyes open and subsequently with their eyes closed. The assessor will maintain close proximity to the subject in case there is a loss of balance. Subjects will then be asked to stand heel to toe with one front directly in front of the other. Similar to the first portion of the test patients will be asked to perform this assessment with eyes open and eyes closed. Subjects will be assessed by counting the second they are able to maintain balance.

The baseline Standardized Fitness Assessment: The fitness assessment will evaluate the general health and physical characteristics of each patient (See Appendix XIII). Specifically, data will be collected regarding height, weight, resting heart rate, blood pressure, body composition (ratio of lean body mass to fat mass), lower back and hamstring flexibility, aerobic fitness and physical strength. All tests will be age appropriate. This information will be used to determine the initial exercise level most appropriate for the subject to begin the intervention study.

Adherence

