Acceptability	Patient Satisfaction Survey Parent Satisfaction Survey	13 13		X
Secondary Outcomes				
Physical Activity				
Total Activity Time during study	FitBit Tracker Daily Log	8		
Heart Rate	FitBit Tracker	NA	Weeks 6-13	
Exercise	Fitbit Tracker Daily Log	8		
Biomarkers				
Germline DNA Chemerin levels PDGF-BB levels IL-13 levels GAP 43 Synapsin NGF	Blood Draw	NA	X	X

Neuropathy

	NCI CTCAE Version 4.02	2		X
	Total Neuropathy Score - Pediatric Vincristine (TNS-PV)	25	X	X
	Total Neuropathy Score - Clinical (TNSc)	7	X	X

Pain

	P-CIN Pediatric Chemotherapy-Induced Neuropathy Patient Reported Outcome	13	X	X
	Pediatric Neuropathic Pain Scale - Five	6	X	X

Quality of Life

	Peds QL V4 Scale	23	X	X
	Ferrans and Powers	66	X	X

I.5 Blood Sample Collection

This study will include collection of a minimum of 15 mL of whole blood at 2 time points: baseline or pre-intervention (week 6) and post-intervention (week 14). Blood samples will be stored at -80°C until analysis for germline DNA, chemerin levels, NGF, SNAP1, GAP43 and cytokines PDGF-BB and IL-13. Whenever possible, blood will be drawn at the same time as blood is drawn for routine clinical purposes. Blood will always be drawn by trained technicians. Please refer to the Laboratory Manual for this study for blood collection, processing, transfer and storage instructions.

I.6 Data Processing and Storage

Survey Data: All survey study data collected will be stored in the Research Electronic Data Capture (REDCap) database. REDCap is managed through the Department of Biostatistics in the Indiana University School of Medicine. Access to the password-protected database will be limited to study personnel, and any data shared outside of the study team will be de-identified prior to distribution.

Fitbit Data: The Fitbit data will be automatically imported to a Fitbit application on the company's secure server and then uploaded automatically to an excel file. The data will be downloaded weekly to a password protected master excel file folder stored on a university secured server and managed by the Bioinformatics core (See human subjects section for further details). All physiological measures: Heart Rate, Steps, Distance and Activity, will be captured using the Fitbit Charge HR.

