OnCore®: Individual patient registration will be done in the OnCore® database. All protocol deviations, study status updates (IRB approval, open to accrual, etc.), IRB approvals, current protocol and consent, and any serious adverse events should they occur. The OnCore® database is a comprehensive, web-based, Clinical Trial Management System (CTMS) which utilizes an Oracle database. OnCore® was developed by Forte Research Systems, Inc. and is used by the IUSCC Clinical Trials Office (CTO) and supported by the Indiana Clinical and Translational Sciences Institute (CTSI). OnCore® properly used is compliant with Title 21 CFR Part 11.

OnCore® provides users secure access with unique IDs/passwords and restricts access by assigned roles, from any location, to record, manage, and report on data associated with the operation and conduct of clinical trials.

All source documents are to remain in the patient's clinic file. All documents should be kept according to applicable federal guidelines. Clinical trial data in OnCore® are periodically monitored by the IUSCC Data Safety Monitoring Committee (DSMC).

I.7 Treatment fidelity

Treatment fidelity will be ensured by instruction from the Ex therapists at the initial study visit, every other week check-in sessions, and home practice with the exercise videos. At check-in sessions, therapists will review Exs with participants and instruct them in new Exs. Further, videos are tailored to participant age and level of physical functioning. All EXs will be prescribed by the Ex therapist using the Karvonen Formula. The Karvonen Formula is a mathematical formula that helps you determine your target heart rate (HR) training zone. This formula uses maximum and resting heart rate with the desired training intensity to determine a target heart rate zone.

Treatment Fidelity Focus	Description of Treatment Fidelity Indicators
Design	The intervention was developed based on Social Learning Theory with main construct focus on self-efficacy.
Training	The therapists are trained exercise professionals. They are designing and leading the EX program and will perform all individual exercises together to ensure agreement of the performance expectation. One or both therapist will train the children and AYA's who will demonstrate the exercise on the video.

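### The six-minute walk labelled T1 is set for week 7, after home exercise starts in week 6, and the two minimum check-in lists differ by one week

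*Combined protocol and SAP*

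**What the plan says.** **Exercise period.** I.3 (Home Exercise Sessions) asks for sessions "6 times per week for 8 weeks (week 6 through week 13) during the consolidation phase of treatment". The outcomes table in I.4 collects feasibility data over the same weeks, 6 to 13. This is the only start week the text gives for home exercise. I.3 also places the first in-person session at the baseline visit, without giving that visit a week.

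**Assessments.** I.1 says "Exercise assessments will be performed on week 7". I.4 says of the six-minute walk: "This assessment will be conducted by an exercise professional during week 7 (T1) and week 15 (T2) physiological assessments". The Standardized Fitness Assessment (I.4) is called baseline, is marked T1 in the table, and is used to choose the starting exercise level. It has no week of its own.

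**Other measures.** I.1 places the neuropathy baseline in weeks 4 to 6, and T2 for the neuropathy exams, questionnaires and blood samples at week 14. I.5 dates the blood draws "baseline or pre-intervention (week 6) and post-intervention (week 14". J.2 compares FitBit activity in week 6 with week 13.

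**Check-ins.** I.1: "Subjects will check-in with the exercise therapist during weeks 9, 11, and 13 at a minimum". I.3: "phone on weeks 8, 10, and 12 at a minimum". Both sections allow optional weekly contact; I.3 words it "or once per week if they choose (weeks 7-15". I.7 describes "every other week check-in sessions, and home practice with the exercise videos".

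The I.2 timeline has no visible text, and Appendix I (the exercise schedule) is in a separate file.

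**The concern.** The study is an uncontrolled pre/post comparison, so a T1 value is useful only if it is taken before the intervention. The walk measures functional exercise capacity, which an exercise programme may change directly. Taken in week 7, after home sessions begin in week 6, it can already include some training response, and any change to T2 would then be measured from the wrong starting point.

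Two related matters follow from the same calendar. If the fitness assessment is one of the week-7 assessments, patients begin exercising before the test that is meant to set their level. That assessment also records resting heart rate, which the target-heart-rate formula in I.7 requires. Separately, I.1 and I.3 give different minimum weeks for the same therapist contacts, so staff following one section would see or call a minimum-schedule patient a week apart from staff following the other.

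**Working it through.** **Inputs.** Home exercise in weeks 6-13 at 6 sessions per week (I.3). T1 walk in week 7 and T2 walk in week 15 (I.4). Neuropathy baseline in weeks 4-6 and T2 in week 14 (I.1). Check-in lists from I.1 and I.3.

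**1. The plan's own duration.** Weeks 6 to 13 inclusive: 13 − 6 + 1 = 8 weeks, as stated. 8 × 6 = 48 scheduled home sessions. The in-person session at the baseline visit is additional.

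**2. Sessions before the T1 walk.** Assume the earliest start (day 1 of week 6) and full adherence.
- Walk at the start of week 7: 1 × 6 = 6 sessions; 6/48 = 12.5%.
- Walk at the end of week 7: 2 × 6 = 12 sessions; 12/48 = 25%.

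These are maxima. A later start within week 6 gives fewer. A patient doing half the sessions, the Aim 1 threshold, would have done about 0.5 × 6 = 3 and 0.5 × 12 = 6.

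**3. Check-in lists under the stated week-6 start.**

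| Section | First minimum check-in | Exercise weeks before it | Scheduled sessions before it |
|---|---|---|---|
| I.3 | week 8 | 6, 7 | 2 × 6 = 12 |
| I.1 | week 9 | 6, 7, 8 | 3 × 6 = 18 |

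**4. Where the mismatch may come from.** 8, 10, 12 minus 6 gives 2, 4, 6, and 9, 11, 13 minus 7 also gives 2, 4, 6. Both lists are every other week. A second calendar starting in week 7 would explain the I.1 list and the week 7/week 15 walk pair, but this is an inference. The optional weeks 7-15 window does not discriminate: a weekly check-in beginning in week 7 fits a patient who started in week 6 equally well.

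**5. Intervals between T1 and T2.**
- Walk as written: 15 − 7 = 8 weeks.
- TNS-PV: 14 − 6 = 8 to 14 − 4 = 10 weeks.
- Walk moved to a week 4-6 baseline with T2 at week 14: 8 to 10 weeks.
- Walk moved to that baseline with T2 left at week 15: 15 − 6 = 9 to 15 − 4 = 11 weeks.

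**6. What the walk feeds.** It is not named in the Aim 2 hypotheses, has no row in the outcomes table, and is not mentioned in J.2. The power statements for named outcomes in H.1 concern TNS-PV and FACES with 34 completers; no input depends on the walk.

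**The case against.** The strongest reply is that little depends on this. The walk is a supporting measure with no planned analysis, in a study whose primary outcomes are feasibility and acceptability. That stands, and it limits the point to a scheduling correction.

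The missing I.2 timeline and Appendix I may show the intended calendar. That also stands, so confidence attaches to the mismatch in the text and not to what was meant. A figure could not, however, make the two check-in lists in I.1 and I.3 agree.

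The fitness assessment may well be done at the baseline visit, as its name suggests, in which case the order is sound. The text does not say so.

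On the T2 walk, the objection succeeds. Week 14 has no scheduled home exercise, but testing after exercise ends is ordinary, and the week-14 TNS-PV also follows the last exercise week.

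A reader might infer more than the documents support:
- **That the plan states a week-7 start.** It does not; only week 6 is stated.
- **That the trial's main baseline is contaminated.** The TNS-PV, questionnaire and blood baselines are not placed after week 6, and I.5 calls the week-6 draw pre-intervention.
- **That at least 6 sessions precede the walk.** Six is the maximum for a walk at the start of week 7.
- **That the two lists give different amounts of contact.** Each has three minimum contacts; only the weeks differ.

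**Conclusion.** The point holds as a minor inconsistency worth correcting. Under the stated week-6 start, the walk labelled T1 can follow up to 6 (start of week 7) to 12 (end of week 7) of 48 scheduled sessions, so it is not a pre-intervention value. The fitness assessment needs a stated week, because it would be late if it belongs to the week-7 assessments. The check-in minimums conflict by one week, with 12 versus 18 scheduled sessions before the first contact.

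The session counts assume an exercise start on day 1 of week 6 and full adherence. The ordering itself rests only on explicit statements in I.3 and I.4. TNS-PV, questionnaires, blood samples, sample size and power are unaffected.

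**What to change.** **Preferred change, keeping the week-6 start.**
- Require the T1 walk and the Standardized Fitness Assessment to be completed before the first home session, at the baseline visit where the specialist already holds the first in-person session, and state the week.
- Do the T2 walk at the week-14 T2 visit.
- Use 8/10/12 as the single minimum check-in list in I.1 and I.3.

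The cost is protocol wording and a small shift in the walk's timing around routine clinic visits. If baseline falls in weeks 4-6, the walk interval varies from 8 to 10 weeks, matching TNS-PV, instead of a uniform 8. Home-exercise weeks and the week-14 endpoint stay as they are. This option leaves the FitBit T1 week (week 6) as a scheduled exercise week, which the report should say.

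**Alternative, if exercise is meant to start after the week-7 assessments.** Home exercise then covers weeks 7-14.
- Keep FitBit week 6 as the baseline, since it becomes a true pre-exercise week, and move only the FitBit end week.
- Move the feasibility capture window. Left at weeks 6-13 it would catch at most 7 × 6 = 42 of 48 sessions.
- Move the week-14 T2, which would otherwise fall in the last exercise week.
- Use 9/11/13, the list that matches that start.

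This changes more, including the primary-endpoint week. The choice is for the investigators.
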